## **3.0 Objectives and Endpoints**

### **3.1 Primary Objective**

The primary efficacy co-outcomes are: a change in the visual analog scale (VAS) pain score and a change in the pain subsection of the knee injury and osteoarthritis outcome (KOOS) score.

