#### **9.3.2 Primary and Secondary Efficacy Analyses**

Eight separate repeated-measures analysis will be performed on the eight efficacy variables described above. Each of the eight variables will be used as a dependent variable. The following model building method will be used for each analysis. Using Statistical Analysis System (SAS) MIXED Procedure (version 9.4; SAS Institute, Cary, NC), a linear mixed model will be fit on each efficacy variable. The model will include site, treatment arm, time on study (baseline and 1, 3, 6, 9

and 12 months on study), and treatment arm by time interaction as fixed effects. Subject ID will be the random effect. A compound-symmetric variance-covariance form in repeated measurements will be assumed and robust estimates of the standard errors of parameters will be used to perform statistical tests and construct 95% confidence intervals. The model-based means are unbiased with unbalanced and missing data, assuming missing data are non-informative. A P-value  $\leq 0.05$  will be considered statistically significant for all the terms in the mixed model. The statistical test for interaction between time on study and treatment will be the overall hypothesis test to determine whether efficacy variables in the four treatment arms changed significantly during 12 months of follow-up. If mean scores in the treatment arms are consistently different or similar over time (i.e., no statistical interaction) then the main effect test for treatment will be used as the primary hypothesis test to compare the treatment arms. The primary study results from this model will be the mean score and 95% confidence interval for each of the 4 treatment arms and the treatment mean differences and 95% confidence intervals.

Assuming a significant treatment effect on efficacy score change is identified (i.e., the interaction test is significant at  $P = 0.05$ ) then the six pairwise treatment comparisons on pain score change will be performed. A Bonferroni correction ( $p=0.05/6=0.0083$ ) for multiple comparisons will be applied. Specific statistical tests on efficacy score change will be done within the framework of the mixed effects linear model. All statistical tests will be 2-sided and adjusted for multiple comparisons. The same Bonferroni method will be used if the statistical interaction between treatment group and time on study is not significant but the main effect test for treatment is significant.

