### **9.3.3 Efficacy Analyses across Subgroups**

The heterogeneity of treatment effects across age, sex, and ethnicity will be evaluated using a statistical test for interaction terms. Specifically, effects of treatment in subgroups will be determined by including the additional interaction terms between treatment and the three subgroups (age, sex, and ethnicity) in the repeated measures model described above for the eight efficacy variables.

The following variables will be treated as categorical variables in all of the linear mixed models.

- Treatment arms: CSI (reference), BMAC, ADP, UCT
- Age:  $\leq 65$  (reference) vs.  $>65$
- Sex: female vs male (reference)

- Ethnicity: Hispanic vs non-Hispanic
- Time: 0, 1, 2, 3, 4, 5 representing baseline and 1, 3, 6, 9 and 12 months follow-up visits

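### Section 9.3.2 can make a treatment main effect that averages in the pre-injection score the primary test, and names no visit for the pairwise tests, although section 9.2 sizes the trial on change at 1 year

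*Combined protocol and SAP*

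**What the plan says.** Section 3.1 gives the co-primary outcomes as "a change in the visual analog scale (VAS) pain score and a change in the pain subsection" of KOOS, without a time point. Section 9.2 and the synopsis size the trial on improvement from baseline to 1 year.

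Section 9.3.2 fits the score itself in a linear mixed model. Section 9.3.3 codes time as "Time: 0, 1, 2, 3, 4, 5 representing baseline and 1, 3, 6, 9 and 12 months follow-up visits", so the pre-injection score is one of six responses.

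The treatment-by-time interaction is the overall test, meant "to determine whether efficacy variables in the four treatment arms changed significantly during 12 months of follow-up". If it is significant, "then the six pairwise treatment comparisons on pain score change will be performed", each at 0.05/6 = 0.0083. The alternative route begins "If mean scores in the treatment arms are consistently different or similar over time" and continues "i.e., no statistical interaction) then the main effect test for treatment will be used as the primary hypothesis test to compare the treatment arms". For that route, "The same Bonferroni method will be used if the statistical interaction between treatment group and time on study is not significant" but the main effect is. The section adds: "All statistical tests will be 2-sided and adjusted for multiple comparisons". No visit or contrast is named for the pairwise tests, and the group means and mean differences that form the primary results carry no time point either.

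**The concern.** There are two linked faults.

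**The fallback tests the wrong quantity.** Randomisation makes the groups equal in expectation before injection. With baseline among the responses, any lasting post-injection difference is therefore itself a treatment-by-time interaction. A true absence of interaction means no treatment effect on change. The situation the fallback is written for, groups apart by the same amount at all six times, describes chance baseline imbalance and not efficacy. The main effect also compares average level, whereas section 3.1 defines the outcome as change.

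**The pairwise contrast is open.** Change could mean change at Month 12, change at any earlier visit, or average change after baseline. The text ties the group comparisons neither to the 1-year effect used for sizing nor to the sustained benefit sought in section 4.2, and it leaves room for the contrast to be settled after the data are seen.

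**Working it through.** **Inputs from section 9.2.** VAS difference 1.5, SD of change 3.5; total KOOS difference 10, SD 20; n = 121 per group in the power statement, 120 planned; 90% retention, so 0.9 × 120 = 108. From 9.3.2: compound symmetry, six times, pairwise level 0.0083.

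**Assumptions.** The documents give no between-visit correlation, so ρ = 0.3, 0.5 and 0.7 are used. Effect profiles are also assumed. One group differs from the other three.

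**Plan's own figures.** A two-sample t-test at n = 121 gives 91.3% (VAS) and 97.2% (KOOS), against 91% and 97% stated. The sizing arithmetic is sound for the 1-year change.

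**What the main effect estimates.** It is the mean difference over six times, with 0 expected at baseline.
- Constant effect d from Month 1: 5d/6. For 0.75, 1.0 and 1.5 points this is 0.63, 0.83 and 1.25.
- Effect proportional to month/12: (0+1+3+6+9+12)/(12 × 6) = 31/72 = 0.43 of the Month 12 effect.

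**How often the fallback is reached.** Residual variance is 3.5²/2 = 6.125. For a constant effect the 15-df interaction test has noncentrality λ = n·d²·(3/4)·(5/6)/6.125, whatever ρ is. With n = 108:
- d = 0.75: λ = 6.20, power 28%, fallback 72%
- d = 1.0: λ = 11.02, power 51%, fallback 49%
- d = 1.5: λ = 24.80, power 92%, fallback 8%
- rising to 1.0 at Month 12: 5/6 is replaced by the sum of squared deviations of the profile, 0.770, so λ = 10.18, power 47%, fallback 53%

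**No true effect (simulated).** The main effect alone rejects in 5.0%. One or other overall test is significant in 9.7–9.8% (formula 1 − 0.95² = 9.75%), but that is not a false-claim rate, because the pairwise step follows. A false pairwise claim per endpoint occurs in 4.7% with one fixed contrast, in about 7.1% if any of the five post-baseline visits may be chosen without further adjustment, and in 3.8% under the fix below. About 3.6% of null trials make a false claim through the fallback. In 0.9/1.3/1.9% of null trials (ρ = 0.3/0.5/0.7) such a claim coincides with a baseline difference at p ≤ 0.05.

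**Power for at least one true pairwise claim (simulated, n = 108, ρ = 0.3/0.5/0.7).** The present plan is read as using Month 12 change on the interaction route. The fix uses the Month 12 score adjusted for baseline, with SD 3.5·√((1+ρ)/2) = 2.82/3.03/3.23.

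| True effect | Present plan | Fix |
|---|---|---|
| Constant 0.75 | 63/41/28% | 44/38/34% |
| Constant 1.0 | 82/67/51% | 73/65/59% |
| Constant 1.5 | 94/93/90% | 98/96/94% |
| Rising to 1.0 at Month 12 | 52/44/40% | 73/65/59% |

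The loss at ρ = 0.3 comes from using one visit, not from taking baseline out of the response. A baseline-adjusted average of the five post-baseline visits has 89/74/62% at constant 0.75, but only 54/39/30% for the rising effect.

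Balanced ANOVA tests on simulated group means stand in for PROC MIXED with robust errors. A check on individual-level data with an estimated baseline slope agreed: constant 0.75 gave 65/41/27% for the present plan and 43/36/33% for the fix.

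**The case against.** - **The fallback seldom decides at the planned effect.** At 1.5 points it is reached in 8% of trials at n = 108 and about 5% at n = 120. Taking 108 at every visit is pessimistic, since the 90% applies at 1 year. At 0.75 points and n = 108, the fallback yields a true pairwise claim in 47/25/11% of trials, fewer than the 72% that reach it. This stands. It limits the first fault to effects smaller than planned, but the unnamed contrast affects every trial that gets to pairwise testing.
- **Error is controlled and power can be better.** This stands for any one pre-specified contrast, and for modest constant effects at low correlation. But no contrast is specified, and the extra power belongs to a test of level.
- **The intended contrast can be inferred.** Sections 9.2 and 1.1 speak of baseline to 1 year, so Month 12 change is a natural reading on the interaction route. That is probably the intention, but 9.3.2 does not say it, and on the fallback route the same reading leads to all-times means.
- **A separate SAP may settle it.** Section 9.3 calls itself a summary of one, and its text is not in the combined document. It may name the contrast. The protocol's own rule making a test of level primary would still need correcting.
- **Month 12 is a choice.** Section 3.1 gives no time, and an average over follow-up is legitimate. Section 9.2 would then have to be restated.

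**Conclusion.** The concern holds and should be fixed. As written, the plan can make a primary claim from a difference in average level that includes the pre-injection score, estimating 5/6 of a constant effect or 0.43 of a linearly rising one. It also leaves the pairwise contrast undefined. The damage is to what the result means. Type I inflation is modest and arises only if the visit is chosen freely (about 7.1% against 4.7% per endpoint), and loss of power depends on the effect profile. The dilution factors follow from the design and the profile alone. The fallback frequencies rest on SD 3.5, compound symmetry, n = 108 and the assumed profiles. The power comparison depends also on ρ, which the documents do not give.

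**What to change.** In 9.3.2, replace the main-effect fallback and the pairwise sentence with:

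> For each co-primary endpoint the primary contrast is the between-group difference at Month 12, adjusted for the baseline score. The four groups are compared at Month 12 (3 df, two-sided 0.05). If this is significant, the six pairwise Month 12 differences are tested at 0.0083.

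Use Months 1, 3, 6, 9 and 12 as the response, with site, treatment, visit, treatment-by-visit and baseline score as fixed effects. Alternatively, keep baseline in the response with its mean constrained equal across groups. Do not use the all-times main effect as a primary test. Report treatment-by-time and the baseline-adjusted average post-baseline effect as supportive. Change the time coding in 9.3.3 to match, and reconcile both sections with the separate SAP.

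**Cost.** Wording only; no new visits or data. Effects seen only before Month 12 become supportive. At ρ = 0.3 power falls from 63% to 44% at constant 0.75 points and from 82% to 73% at 1.0. At ρ = 0.5 these two cases are about level. Power rises at ρ = 0.7, at the planned 1.5 points, and for an effect that builds toward Month 12. If the team prefers the average post-baseline effect as primary, power for a constant effect is higher, but 9.2 must then be restated for that contrast.

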### 1.1 Synopsis

Title of Study	Randomized multicenter phase 3 single-blind trial comparing the efficacy of corticosteroid control to mesenchymal stem cell preparations from autologous bone marrow concentrate (BMAC), adipose derived stem cells in the form of Stromal Vascular Fraction (SVF), and third party human mesenchymal stem cells manufactured from umbilical cord tissue (UCT) for the treatment of unilateral Knee Osteoarthritis (OA).
Study Objectives	To identify a superior source of stem cells for the treatment of osteoarthritis and validate its advantages over corticosteroid injections as traditional gold standard treatment. The primary efficacy co-outcomes are: a change in the visual analog score (VAS) pain score and a change in the pain subsection of the knee injury and osteoarthritis outcome (KOOS) score. Secondary endpoints include total KOOS score, Magnetic Resonance Imaging (MRI) and additional patient reported outcomes (PROs).
Study Design	Multicenter prospective single-blinded randomized controlled clinical trial. The study will include a parallel design using a blocked central randomization scheme of 1:1:1:1. Subjects will be allocated to three different arms with a 3:1 assignment. Autologous bone marrow concentrate (n=120): corticosteroid (n=40), umbilical cord tissue (n=120): corticosteroid (n=40), and adipose derived SVF (n=120): corticosteroid (n=40).

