#### **9.2 Sample Size Determination**

The total estimated sample size for the proposed intention-to treat, parallel-group, multicenter, randomized, controlled trial is 480 subjects. The primary endpoints are Visual Analog Scale (VAS) pain score and the pain subsection of the Knee Injury and Osteoarthritis Outcomes (KOOS). The sample size calculations are based on improvements (from baseline to 1-year) in the visual analog scale (VAS) pain score and total KOOS. Total KOOS was used as a proxy and should ensure that the study is amply powered.

Assuming a decline of 1 point on average in pain in the Control arm (corticosteroids) and a decline on average of 2.5 points in a treatment arm (mesenchymal stem cells) and an estimated standard deviation on change of 3.5, the proposed sample sizes (n=121 subjects

per group or 484 total subjects) will provide 91% power to detect a difference on change of 1.5 points at the two-sided 5% significance level if the true difference between treatment groups is 1.5 points (two-sided two-sample equal variance t-test).

Assuming an increase of 10 points on average in total KOOS in the Control arm (corticosteroids) and an increase on average of 20 points in a treatment arm (mesenchymal stem cells) and an estimated standard deviation on change of 20, the proposed sample sizes (n=121 subjects per group or 484 total subjects) will provide 97% power to detect a difference on change of 10 points at the two-sided 5% significance level if the true difference between treatment groups is 10 points (two-sided two-sample equal variance t-test).

Each of the four participating sites will accrue 30 subjects to each of the 4 treatment groups. Cohort retention is expected to be 90% at 1-year.

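### The six pairwise comparisons are all held to a fixed Bonferroni 0.0083; this is valid, but Holm's step-down rule gives the same 5% control within each variable with more power

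*Combined protocol and SAP*

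**What the plan says.** Section 9.3.2 fits a separate mixed model to each of eight efficacy variables, two of them primary (VAS pain and KOOS pain). The pairwise tests can be reached by two routes. If "the interaction test is significant at" 0.05, all six pairs among the four groups are compared: "then the six pairwise treatment comparisons on pain score change will be performed". The threshold is then fixed: "A Bonferroni correction ( $p=0.05/6=0.0083$ ) for multiple comparisons will be applied". On the other route, "The same Bonferroni method will be used if the statistical interaction between treatment group and time on study is not significant" but the main effect of treatment is. No ordering of p-values and no step-down is described on either route.

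The section adds that "All statistical tests will be 2-sided and adjusted for multiple comparisons". The results it promises are group means and "the treatment mean differences and 95% confidence intervals"; it does not say that these intervals are adjusted or simultaneous.

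The Synopsis (section 1.1) gives the aim: "To identify a superior source of stem cells for the treatment of osteoarthritis and validate its advantages over corticosteroid injections".

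**The concern.** Single-step Bonferroni applies the threshold meant for the smallest of six p-values to all six. Once one pair has been rejected, fewer true equalities can remain, and the later thresholds can be relaxed without raising the family-wise error above 5%. Holm's rule does this using only the count of remaining tests. Shaffer's rule also uses the logical links among pairs of means.

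The loss falls on conclusions that need several pairs to be significant together. The stated aim is of that kind: a best source has to be separated from the other sources and from steroid. The power lost could be recovered without adding subjects, visits or data.

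**Working it through.** **Inputs.** From section 9.2: VAS change in the control arm ("a decline of 1 point on average in pain in the Control arm (corticosteroids"), against 2.5 points in a cell arm, so a difference of 1.5; SD of change 3.5; total KOOS difference 10 with SD 20; 121 per group in the power statements; 30 per group at each of four sites, so 120; retention 90%, so 0.9 × 120 = 108. From section 9.3.2: six pairs, two-sided, 0.05/6.

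**The plan's own figures.** 0.05/6 = 0.00833, as stated. For VAS with 121 per group the noncentrality is 1.5 / (3.5 × √(2/121)) = 3.33, and the two-sample t-test at two-sided 0.05 has power 91.3%. For KOOS it is 10 / (20 × √(2/121)) = 3.89, with power 97.2%. Both agree with the stated 91% and 97%, which are at an uncorrected 5%.

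**The thresholds, from smallest p-value to largest, stopping at the first failure.**
- Bonferroni: 0.0083 for all six (no ordering).
- Holm, 0.05 divided by 6, 5, 4, 3, 2, 1: 0.0083, 0.0100, 0.0125, 0.0167, 0.0250, 0.0500.
- Shaffer, 0.05 divided by 6, 3, 3, 3, 2, 1: 0.0083, 0.0167, 0.0167, 0.0167, 0.0250, 0.0500.

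**Where Shaffer's constants come from.** Four means can be all equal (6 true equalities), split 3+1 (3 true), split 2+2 (2 true), have one equal pair (1 true), or all differ (0 true). After the first rejection at most 3 equalities can still be true. That bound holds while 5, 4 or 3 tests remain, and then falls to 2 and to 1.

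**Simulation.** 200,000 four-group trials per scenario, normally distributed 1-year change, and t-tests with variance pooled over the four groups. Adding a 3-df F test at 0.05 in front of the pairs did not change the all-three results at 108 per group.

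| Event | n per group | Bonferroni | Holm | Shaffer |
|---|---|---|---|---|
| All three cell products beat steroid, VAS | 120 | 54% | 60% | 64% |
| Same | 108 | 46% | 52% | 57% |
| All three beat steroid, total KOOS | 120 | 76% | 81% | 84% |
| Same | 108 | 69% | 74% | 78% |
| One named cell–steroid pair, VAS (all three products work) | 120 | 75% | 78% | 81% |
| Only one source works (1.5 points) and it beats all three other groups, VAS | 120 | 54% | 60% | 64% |
| At least one cell–steroid win, VAS (all three products work) | 120 | 92.5% | 92.5% | 92.5% |

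The last row does not move because every rule starts at 0.05/6, and in that scenario the first rejection is almost always a cell–steroid pair.

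**Family-wise error within one variable.** With three cell arms equally better than steroid (VAS, 120 per group): 2.3% (Bonferroni), 3.6% (Holm) and 4.4% (Shaffer). With no differences at all: 4.2% for each. No scenario run exceeded 4.5%.

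**The case against.** **Bonferroni is valid, and choosing it is legitimate.** This stands. The point concerns efficiency; it does not identify an error. The gain with Holm is moderate: about 6 points for the joint VAS events and 3 points for one named pair.

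**Bonferroni has something to offer in return.** It has directly matching simultaneous intervals; step-down tests have no simple ones. After a change, a pair could be declared significant while its Bonferroni interval (99.17% coverage, 1 − 0.05/6) includes zero. This matters because the plan presents differences with intervals as its main result. However, section 9.3.2 promises only plain 95% intervals, so the plan does not use the advantage it would give up.

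**There are two primary variables and no rule linking them.** All the 5% statements are per variable. With three equal cell arms, the chance of a false source-versus-source claim on either VAS or KOOS is about 3.4–4.5% with Bonferroni, 5.4–7.4% with Holm and 6.3–8.6% with Shaffer, for assumed correlations between the two from 0.9 down to 0. Here total KOOS stands in for KOOS pain, as in section 9.2. In that scenario Bonferroni's slack happens to absorb the second variable. The plan neither claims joint control nor provides it by design, but the cost is real and should be known.

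**All-three success is not a criterion in the documents.** Correct. The Synopsis asks for a superior source and its advantage over steroid. The case does not rest on the all-three event: where only one source works, the gain for that source beating every other group is the same.

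**A reader might infer that the overall test and Bonferroni together make the plan doubly conservative.** The documents do not support that. The pairs can also be reached through the main effect when the interaction is not significant, so two 5% tests can open the way (in about 1 − 0.95² = 9.75% of null trials if they are independent). How conservative the whole is depends on which contrast is tested on the second route, which section 9.3.2 does not specify.

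**Conclusion.** The fixed 0.0083 is valid but less powerful than a step-down rule with the same 5% guarantee within each efficacy variable. Under the plan's VAS figures the gain in joint conclusions is about 6 points with Holm and 10 to 11 with Shaffer, at either 120 or 108 per group. For one named pair at 120 it is about 3 and 6 points.

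These sizes assume tests on 1-year change, equal variances, and either three equally effective products or a single effective one. Holm's superiority does not depend on those assumptions, because it rejects whatever Bonferroni rejects and controls the error under any dependence.

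A reader might go further and infer that the power is given up for no return, or that the interaction test could be reduced to a supportive role. Neither follows. Bonferroni's matching intervals and its slack across two unlinked primaries have some value. Section 9.3.2 also makes the interaction test its overall hypothesis test, so demoting it would change the declared primary analysis.

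Section 9.3 describes itself as a summary of a SAP. Only the text supplied was checked; if a fuller SAP already sets a step-down rule, section 9.3.2 should be aligned with it.

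**What to change.** In section 9.3.2, leave the overall test and both routes as planned. On both routes, replace the fixed 0.0083 with Holm's step-down for the six ordered p-values (0.05/6, 0.05/5, 0.05/4, 0.05/3, 0.05/2, 0.05), stopping at the first failure. Shaffer's constants for four groups (6, 3, 3, 3, 2, 1) are the stronger alternative. Choose one, and record the choice before any unblinded results are seen.

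Add two sentences. One should say which intervals accompany the pairwise tests and that the step-down test, not the interval, decides significance. The other should say that control is within each efficacy variable and does not cover the two primary variables jointly. If joint control is wanted, it needs its own rule.

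The cost is a change of wording in the protocol and SAP and of the adjustment step in the analysis program. The price in interpretation is the loss of simple matching simultaneous intervals and the use of the slack described above.
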